6.5 Discontinuation/ Withdrawal of Participants from Study Treatment

Each participant has the right to withdraw study at any time. In addition, the investigator may discontinue a participant from the study at any time if the investigator considers it necessary for any reason including:

- Pregnancy
- Ineligibility (either arising during the study or retrospective having been overlooked at screening)
- Significant protocol deviation
- Significant non-compliance with study requirements
- An adverse event, adverse device effect, serious adverse device effect or unanticipated adverse device effect which results in cessation of the CLE test or inability to continue to comply with study procedures
- Consent withdrawn
- If the participant cannot wear the headgear, e.g. it does not fit.
- If the CLE test is unable to allow a diagnosis of EILO to be confirmed or ruled out due to reasons unrelated to the headgear, e.g. the participant cannot tolerate the endoscopy.

Withdrawn participants will be replaced.

The reason for withdrawal will be recorded in the Case Report Form (CRF).

If the participant is withdrawn due to an adverse event, the investigator will arrange for follow-up visits or telephone calls until the adverse event has resolved or stabilised.

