6.4.4 Subsequent assessments

Following the consultation appointment, the participant will attend one investigation appointment to undergo the CLE test on-site at the Outpatient Department, Alexandra Wing, Broadgreen Hospital. There will be no follow-up assessments.

On the day of the investigation appointment, the Principal Investigator will address any questions or concerns before the investigation begins. If the participant still wishes to partake in the study, signed consent will be obtained from the participant. The right of the participant to refuse to participate without giving reasons will be respected. After the participant has entered the study the clinician remains free to give alternative treatment to that specified in the protocol at any stage if he/she feels it is in the participant's best interest, but the reasons

for doing so should be recorded. In these cases, the participants remain within the study for the purposes of data analysis.

Eligibility will be reviewed for any changes, ensuring that the participant meets the inclusion criteria and none of the exclusion criteria apply. As part of this, the circumference of the participant's head around the forehead will be measured and recorded. Signed consent will then be obtained. The participant will then undergo the CLE test following standard clinical practice.

The order of events of the aspects of the investigation related to the headgear will be:

1. The headgear is prepared for use.
2. The headgear is fitted onto the participant's head.
3. The endoscope is inserted into the participant.
4. The endoscope is fitted onto the headgear.
5. The CLE test is carried out.
6. The endoscope is removed from the headgear.
7. The endoscope is removed from the participant.
8. The headgear is removed from the participant.
9. The headgear is cleaned and stored.

Following completion of the CLE test, the participant will complete a questionnaire:

- How tolerable was the headgear during the investigation?
 - 1) Highly intolerable
 - 2) Intolerable
 - 3) Tolerable
 - 4) Highly tolerable
- Please tell us any concerns about the headgear, thinking about how comfortable it was, how hot your head felt, the weight of the headgear, how secure it felt and the impact of the headgear on your performance during the investigation.

Following the appointment, the clinician will complete a questionnaire including:

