9.7 Inclusion in Analysis

All eligible participants will be included in analysis.

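### Sections 6.4.4, 6.5 and 9.7 do not settle whether a performed test with a protocol departure stays in the analysis, and 6.5 lets that be decided after the image result is known

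*Combined protocol and SAP*

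**What the plan says.** Four places in the protocol bear on this.

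- **Section 6.4.4, retention.** After entry, "the clinician remains free to give alternative treatment to that specified in the protocol at any stage" if this is judged to be in the participant's best interest, with reasons recorded. The consequence for the data is explicit: "In these cases, the participants remain within the study for the purposes of data analysis".
- **Section 6.5, withdrawal.** Here "the investigator may discontinue a participant from the study at any time if the investigator considers it necessary for any reason including" a list of grounds. Two of them are "Significant protocol deviation" and "Significant non-compliance with study requirements". Neither is defined. The section adds: "Withdrawn participants will be replaced". The reason for withdrawal goes in the CRF.
- **Section 9.7, analysis set.** The whole rule is: "All eligible participants will be included in analysis". Withdrawn, replaced and deviating participants are not mentioned.
- **Timing.** Section 4.2 describes the endoscope image as live. For the primary outcome, section 6.4.4 says: "Following the appointment, the clinician will complete a questionnaire including" the question on whether the image was adequate.

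**The concern.** A clinician's best-interest departure may also be one that the investigator regards as a significant deviation. Section 6.4.4 then keeps the participant for analysis, while 6.5 allows withdrawal and replacement. No section says which rule prevails. For deviations outside that overlap, only the undefined ground in 6.5 applies.

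Nothing requires the withdrawal decision to be made before the image result is known, or by someone unaware of it. The primary outcome is a proportion of about 30 yes/no results, so each inclusion decision carries weight. Two analysts could follow the plan in good faith and report different primary results from the same tests. If failing tests were withdrawn more readily than successful ones, the device would look better than it is.

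**Working it through.** **Inputs.** n = 30 (section 9.2), reference proportion 49/50 = 0.98 (section 9.1), significance level 0.01 (section 9.3; sidedness not stated). Section 9.2 sets 30 on practical grounds without a power calculation, so there is no figure of the plan's own to reproduce. The true success rate p and the share m of failing tests that is withdrawn and replaced are assumptions.

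**Step 1: the rules side by side.**

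| Event | 6.4.4 | 6.5 | 9.7 |
|---|---|---|---|
| Alternative treatment in the participant's best interest, not regarded as a significant deviation | Kept | No specific ground; open discretion remains | Kept if eligible |
| Same, but regarded as a significant deviation or non-compliance | Kept | May be withdrawn and replaced | Silent on withdrawn participants |
| Other significant deviation or non-compliance | Not covered | May be withdrawn and replaced | Silent on withdrawn participants |

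The direct conflict is in the second row. In the third row there is no conflict with 6.4.4, but the fate of the data is still not stated.

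**Step 2: can one decision change the primary test?** Under p0 = 0.98 the number of failures in 30 is binomial with probability 0.02.

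- P(at most 2 failures) = 0.9783, so 27/30 has lower-tail p = 1 − 0.9783 = 0.0217.
- P(at most 3 failures) = 0.9971, so 26/30 has lower-tail p = 1 − 0.9971 = 0.0029.

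The exact two-sided p-values are the same for these two results. At 0.01, 26/30 is significantly below 98% and 27/30 is not. Withdrawing one of four failures and replacing it with a success moves the result across that line.

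**Step 3: size of bias if only failures are removed.** If a share m of failures is replaced and no successes are removed, the expected observed proportion is

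p / [p + (1 − p)(1 − m)] = p / [1 − m(1 − p)].

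With p = 0.90:

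- m = 0: 0.90 / 1 = 90.0%
- m = 1/3: 0.90 / (1 − 0.0333) = 93.1%
- m = 1/2: 0.90 / 0.95 = 94.7%

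The chance of a result of 26/30 or worse, that is, of finding the device below 98% at the 0.01 level, falls from 35% at m = 0 to 7% at m = 1/2.

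**The case against.** The case on the other side has five parts.

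1. **Scope of 6.4.4.** A reader might infer that the two sections contradict each other for every departure from protocol. They do not. Section 6.4.4 covers only alternative treatment in the participant's best interest, and 6.5 is permissive. One can read the first as the specific rule and the second as the general one. This stands, and it confines the conflict to the overlap. The text does not state that order of precedence, however.
2. **Data are not expressly dropped.** Section 6.5 never says that a withdrawn participant's data leave the analysis, and a deviator may still be eligible under 9.7. This also stands: exclusion is inferred from replacement within a planned 30. But if withdrawn tests stay in and are also replaced, the denominator exceeds 30. Both readings remain open.
3. **Direction of bias.** A reader might infer that deviations cluster where the headgear performs badly, so that removals would fall mainly on failures. The documents say nothing of the kind. If deviations are unrelated to image quality, removing and replacing them does not bias the proportion. The values of m above are therefore illustrations.
4. **Perfect versus near-perfect results.** It is tempting to stress that 30/30 and 29/30 lie on either side of 98%. That contrast changes no test decision: the upper-tail p for 30/30 is 0.545 and the lower-tail p for 29/30 is 0.455. The contrast that matters is 26/30 against 27/30.
5. **Traceability.** Reasons for withdrawal are recorded in the CRF. This makes removals visible but does not prevent selection.

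**Conclusion.** The concern holds in a limited form. The plan has no single rule for a performed test that involves a protocol departure. Sections 6.4.4 and 6.5 conflict where a departure fits both, and 9.7 does not resolve it. The wording permits withdrawal and replacement after the image result is known; it does not show that this is intended or usual.

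One such decision can turn a significant shortfall (26/30, p = 0.0029) into a non-significant one (27/30, p = 0.022). Upward bias depends on removals favouring failures. Under that assumption, and with an assumed true rate of 90%, the expected proportion runs from 90.0% with no removal to 94.7% with half of the failures removed. The gap in the rules does not depend on that assumption, and it should be closed before results accrue.

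**What to change.** Reconcile 6.4.4, 6.5 and 9.7 with one rule fixed in advance:

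- **After the CLE test has started with the headgear:** a protocol deviation, non-compliance or any other withdrawal at the investigator's discretion, including under the open wording of 6.5, may end participation. It does not remove the test from the primary, usability or tolerability analyses and does not trigger replacement.
- **After fitting but before the test starts:** fitting is step 2 and the test is step 5 in 6.4.4, so a participant withdrawn on these grounds in between has no CLE test. Such a participant may be replaced, is outside the primary denominator, and is reported with the reason.
- **Handled under their own rules:** withdrawal of consent by the participant, and the separate ground for non-diagnostic tests whose cause is not the headgear.
- **Reporting:** list all deviations, and show the result without those tests as a sensitivity analysis only.

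The cost is a few sentences in 6.5 and 9.7, a deviation listing and one extra analysis. The downside is that a few tests not run exactly to protocol stay in the primary proportion, which may make it slightly less favourable. The change concerns data handling only and leaves clinical discretion as it is.

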4. BACKGROUND AND RATIONALE

4.1 Condition

Exercise-induced laryngeal obstruction (EILO) is a condition in which closure of the larynx occurs during high-intensity exercise. The reduction in airflow due to airway narrowing results in breathlessness and wheeze, and the patient may also report a cough or throat discomfort that can persist for some time (Hall, et al., 2016).

Whilst symptoms usually resolve soon after stopping exercise, an episode of EILO can impact on athletic performance and in competitive sports people can thereby impact on their careers. In all individuals, sudden onset EILO can lead to breathlessness inducing significant fear, panic, loss of control and pain (Carel, et al., 2015).

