8.1.2 Adverse Event (AE)

Any untoward medical occurrence, unintended disease or injury or any untoward clinical signs (including an abnormal laboratory finding) in subjects, users or other persons, whether or not related to the investigational medical device and whether anticipated or unanticipated.

This includes events related to the investigational device or the comparator and events related to the procedures involved (any procedure in the study protocol). For users or other persons, i.e. where the medical occurrence, unintended disease or injury is not in the subject, this definition is restricted to events related to the use of investigational medical devices or comparators.

No potential AEs are identified.

The categories of adverse events are shown in Table 1.

³ Source: BS EN ISO 14155:2020 Clinical Investigation of Medical Devices for Human Subjects – Good Clinical Practice.

Table 1: Categories of adverse events (taken from BS EN ISO 14155:2020 Table F.1)

Adverse events	Non-device-related	Device- or investigational procedure-related	
Non-serious	Adverse event (AE) ^a (3.2)	Adverse device effect (ADE) ^c (3.1)	
Serious	Serious adverse event (SAE) ^b (3.45)	Serious adverse device effect (SADE) (3.44)	
		Anticipated	Unanticipated
		Anticipated serious adverse device effect (ASADE) ^c (3.1, Note 1 to entry)	Unanticipated serious adverse device effect (USADE) (3.51)

^a Includes all categories.
^b Includes all categories that are serious.
^c Includes all categories that are related to the device or the investigational procedure.

8.1.3 Serious Adverse Event (SAE):

SAE is an adverse event that led to any of the following:

- death
- foetal distress, foetal death or congenital abnormality or birth defect including physical or mental impairment.
- serious deterioration in the health of the subject, users or other persons as defined by one or more of the following:
 - a life-threatening illness or injury
 - a permanent impairment of a body structure or a body function including chronic diseases
 - in-patient or prolonged hospitalisation
 - medical or surgical intervention to prevent life-threatening illness or injury, or permanent impairment to a body structure or a body function

Planned hospitalisation for a pre-existing condition, or a procedure required by the Study Protocol, without serious deterioration in health, is not considered a serious adverse event.

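### Section 6.5 lets a CLE test stopped by any adverse event be withdrawn and replaced, whether or not the image had already settled the diagnosis, so valid successes and headgear failures can both leave the primary denominator

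*Combined protocol and SAP*

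**What the plan says.** The list of grounds in section 6.5 opens by saying that "the investigator may discontinue a participant from the study at any time if the investigator considers it necessary for any reason including" the items that follow. One item is "An adverse event, adverse device effect, serious adverse device effect or unanticipated adverse device effect which results in cessation of the CLE test". It carries no condition on cause or on whether the test had already given its answer. The last item is narrower: "If the CLE test is unable to allow a diagnosis of EILO to be confirmed or ruled out due to reasons unrelated to the headgear". The clinician questionnaire in section 6.4.4 repeats that narrower rule beside the image question. Section 6.5 then states, for all grounds alike, "Withdrawn participants will be replaced".

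The primary outcome (6.2.1) is the proportion of tests with an image adequate for diagnosis, so a positive test with a good image is a success. Section 9.7 puts all eligible participants into the analysis and does not mention withdrawals. Section 6.4.4 expressly keeps in the analysis only those given alternative treatment.

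Section 8.1.2 defines an adverse event as "Any untoward medical occurrence, unintended disease or injury or any untoward clinical signs", "whether or not related to the investigational medical device and whether anticipated or unanticipated", and then says "No potential AEs are identified". Section 4.1 says that "sudden onset EILO can lead to breathlessness inducing significant fear, panic, loss of control and pain".

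**The concern.** The adverse-event ground separates tests by why they stopped. The primary outcome separates them by whether the image was adequate. Because these are different questions, the ground can remove a test whose primary result is already known, in an uncontrolled study with 30 planned participants.

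Two kinds of valid result are exposed. One is the stopped test that had already answered the image question. This might include a test stopped by EILO symptoms, which section 8.1.2 neither names nor exempts. The other is the test that gave no diagnosis because a headgear effect stopped it, which is the failure the endpoint exists to count. Losing the first understates device performance, and losing the second overstates it. Replacement fills the gap in either case, so the final 30 would not show the loss unless withdrawals are reported by reason.

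**Working it through.** **What the text permits for a started test stopped by an adverse event**

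| Image question | Cause of stop | Adverse-event ground, 6.5 | Last ground, 6.5, and note in 6.4.4 | Primary result at risk |
|---|---|---|---|---|
| Answered | Any | May be withdrawn | Does not apply | Success lost |
| Not answered | Headgear | May be withdrawn | Does not apply | Failure lost |
| Not answered | Unrelated to headgear | May be withdrawn | Applies | None; uninformative about the headgear |

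Only the third row matches the narrower rule. The first two rows are the gap.

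**Inputs.** From the documents: n = 30 (9.2), reference 49/50 = 0.98 (9.1), significance level 0.01 (9.3). The sample size is set by feasibility, so there is no plan calculation to reproduce. The documents do not give the true success rate p, the share q of successes withdrawn or the share r of failures withdrawn. All three are assumed below.

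**Retained proportion**

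p(1−q) / [p(1−q) + (1−p)(1−r)]

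The retained odds of success are the true odds times (1−q)/(1−r). The proportion falls if q > r, rises if r > q, and is unchanged if q = r. With p = 0.95:

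- q = 0.3, r = 0: 0.665/(0.665 + 0.050) = 0.930
- q = 0, r = 0.5: 0.950/(0.950 + 0.025) = 0.974
- q = 0.3, r = 0.1: 0.665/(0.665 + 0.045) = 0.937
- q = 0.1, r = 0.3: 0.855/(0.855 + 0.035) = 0.961

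**Effect on the test.** I assume an exact binomial test, since section 9.1 does not name the version or the sidedness. Against 0.98, 30 of 30 gives a one-sided p of 0.545, so no result can show performance above the reference. In the other direction, 3 failures give p = 0.0217 and 4 failures give p = 0.0029, so rejection needs at least 4 failures in 30.

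| True p | P(≥4 failures), none withdrawn | q = 0.3, r = 0: retained; P(≥4) | q = 0, r = 0.5: retained; P(≥4) |
|---|---|---|---|
| 0.98 | 0.0029 | 0.972; 0.0098 | 0.990; 0.0002 |
| 0.95 | 0.061 | 0.930; 0.155 | 0.974; 0.007 |
| 0.90 | 0.353 | 0.863; 0.603 | 0.947; 0.071 |

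**Recruitment.** If only successes are withdrawn, retaining 30 needs 30/(1−pq) tests. With p = 0.95 and q = 0.3 this is 30/0.715, or 42 after rounding up, in a study limited to 30 by recruitment.

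**EILO symptoms alone.** Assume that 20–60% of those tested have EILO and 25–75% of these stop because of symptoms. That is 30 × 0.20 × 0.25 = 1.5 to 30 × 0.60 × 0.75 = 13.5 tests, a share f of 5–45%. If all of these tests are diagnostic, all are withdrawn, and the rest succeed at rate s, the proportion falls by f(1−s). This is 0.05 × 0.02 = 0.1 point to 0.45 × 0.06 = 2.7 points. One participant in 30 is 3.3 points.

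**The case against.** The strongest reply is that a successful positive test would not be lost in practice. An episode that the test sets out to observe is arguably neither untoward nor unintended, and "No potential AEs are identified" suggests that the authors did not count it as an adverse event. No section says that an episode stops the test, and a test that ends once the response is seen can be read as complete. Withdrawal is optional, and there is little reason to withdraw someone whose test gave an answer. The note in 6.4.4, the text closest to the endpoint, removes only tests that gave no diagnosis for unrelated reasons. Section 9.7, read literally, keeps every eligible participant. Sections 9.4 and 15 end the study on serious device effects, so replacement matters mainly for less serious ones.

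Much of this stands. A reader might infer that section 8.1.2 makes an EILO attack an adverse event, so that positive tests will leave the analysis and performance will be understated. The documents do not support that. It is one reading of the definition, the loss depends on discretion, and exclusion is inferred from replacement. The direction is open too: if symptom-limited participants are harder to image, removing them could raise the proportion. Nor do the documents show that such symptoms would hide headgear effects, since device effects are classified separately and both questionnaires ask for headgear concerns.

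What the reply does not remove is the gap in the text. The last ground of 6.5 shows how to limit withdrawal to uninformative tests, and the adverse-event ground lacks that limit. The discretion can be used once the image has been seen. Sections 6.5 and 9.7 are not reconciled.

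**Conclusion.** The point holds as a gap in the rule for the primary denominator. It is not a demonstrated bias. Under 6.5, a stopped test with a known primary result can be withdrawn and replaced, whether that result is a success or a headgear-caused failure. The net direction depends on which is withdrawn more often, and the documents do not say.

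The sizes above are illustrations under assumed rates. The EILO-only scenario stays below one participant in 30 even at its extreme, and it assumes that every such test is both diagnostic and withdrawn. Selective loss of failures can be larger: at an assumed p = 0.90 and r = 0.5, the retained proportion is 4.7 points too high (0.947 against 0.900). The case for changing the rule rests on closing an avoidable choice at almost no cost.

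**What to change.** 1. Amend the adverse-event ground in 6.5, and section 9.7 to match. Every participant whose CLE test was started stays in the primary denominator, is scored on the image question in 6.4.4 and is not replaced, even if an adverse event stopped the test.
2. State that a test that is non-diagnostic because of the headgear counts as a failure.
3. Among tests stopped by an adverse event, withdraw and replace only those that are non-diagnostic for reasons unrelated to the headgear, as the last ground of 6.5 and the note in 6.4.4 already provide.
4. Report all withdrawals by reason.
5. Leave adverse-event recording and reporting as they are. The follow-up sentence that closes 6.5 is tied to withdrawal, so reword it so that the existing follow-up is not lost. The sponsor should also reconcile "No potential AEs are identified" in 8.1.2 with the symptoms described in 4.1.

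The participant's own right to withdraw and the grounds on consent and ineligibility are not affected. The cost is a few sentences in an amendment. The downside is that the clinician must judge whether a stopped test had already answered the image question.

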4.4 Rationale for Current Study

A headgear is necessary to carry out CLE tests for the investigations of EILO, as the endoscope must be kept stable for both image quality and patient safety. There is no commercial option existing on the market at present, and other centres have manufactured their headgear in-house (Liverpool Heart and Chest Hospital (LHCH), Royal Brompton Hospital).

Without a specialised headgear it is not possible to carry out CLE tests at LUHFT, and patients are sent for investigations at LHCH. This study is an essential step in improving the care that can be offered by LUHFT for sufferers of EILO. Evaluating the in-house design of headgear is necessary to support its safe and effective clinical use in accordance with the Medical Device Directive (MDD) 93/42 and in the spirit of the European Medical Device Regulations (MDR) 2017/745. By producing an in-house manufactured headgear, it will enable LUHFT to provide an additional service for patients, avoiding the inconvenience to them of having to travel further afield.

Therefore, the hypothesis for this study is that the HALOS headgear is sufficiently effective for clinical use, and that the risks are understood adequately for an accurate benefit/risk ratio evaluation.

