5. OBJECTIVES

5.1 Primary Objective

Ensure the HALOS headgear is suitable for facilitating CLE tests.

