6.2 Primary and Secondary Endpoints/Outcome Measures

6.2.1 Primary Outcome Measure

Device effectiveness, measured by the proportion of CLE tests where the endoscopy image was clear and stable enough to allow a diagnosis of EILO to be confirmed or ruled out.

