6.3.3 Exclusion Criteria

The participant may not enter the study if ANY of the following apply:

- Pain, sore areas, broken skin at the site of contact with the headgear.
- Devices, e.g. cochlear implants, that impede the use of the headgear.
- Head circumference is less than 50cm or greater than 63cm, reflecting the 3rd centile for females and 97th centile for males, respectively (Bushby, 1992).
- Exclusion criteria for endoscopy procedures:
 - Skull base/facial surgery or fracture within the previous six weeks
 - Major or life threatening epistaxis within the previous six weeks
 - Trauma to nasal cavity secondary to surgery or injury within the previous six weeks
 - Sino-nasal and anterior skull base tumours/surgery
 - Nasopharyngeal stenosis
 - Craniofacial anomalies
 - Hereditary haemorrhagic telangiectasia
 - Severe movement disorders and/or severe agitation
 - Vasovagal history
 - Bleeding risks
- Any other exclusion criteria as identified by the current endoscopy procedure.

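### Section 6.5 lets headgear misfits and tests stopped by non-serious device effects be withdrawn and replaced, so the reported proportion can overstate suitability

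*Combined protocol and SAP*

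**What the plan says.** The primary objective (5.1) is to "Ensure the HALOS headgear is suitable for facilitating CLE tests", and 4.4 states that "the hypothesis for this study is that the HALOS headgear is sufficiently effective for clinical use". The primary outcome (6.2.1) is "measured by the proportion of CLE tests where the endoscopy image was clear and stable enough" to settle the diagnosis. Its unit is therefore the CLE test.

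Section 6.5 gives the investigator discretion to discontinue participants. Two of the listed grounds can be caused by the device:

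- "If the participant cannot wear the headgear, e.g. it does not fit"
- "An adverse event, adverse device effect, serious adverse device effect or unanticipated adverse device effect which results in cessation of the CLE test"

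A further ground is a non-diagnostic test for reasons that have nothing to do with the headgear. The section then says, without distinguishing between grounds, "Withdrawn participants will be replaced". The reason for each withdrawal goes in the CRF.

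Four other places bear on the point:

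- A note beside the clinician's image question in 6.4.4 repeats that non-diagnostic tests lead to withdrawal when the cause is unrelated to the headgear.
- Section 9.7 puts every eligible participant in the analysis.
- Section 9.5 allows missing data to be ignored if missing completely at random and at most 5%, and calls for imputation if missing at random.
- Sections 9.4 and 15 end the study for serious device-related events, and section 15 also does so for deficiencies that might have led to one.

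**The concern.** A headgear that cannot be worn, or whose effects stop the test before the larynx has been seen adequately, has not facilitated the test. These are outcomes of the device and not incidental dropouts. If such participants are withdrawn, replaced and left out, the primary proportion is conditional on the headgear having been wearable and having lasted long enough for a diagnosis.

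The two kinds of case differ. For device-effect stops the plan contradicts itself: 6.5 permits removal and replacement, while 6.2.1, the 6.4.4 note and 9.7 imply retention and a failure. Misfits lie outside the endpoint altogether, so the endpoint is narrower than the objective that it serves.

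Two analysts following this protocol could report different proportions from the same participants. The result feeds the clinical evaluation and the risk log (section 16). The participant tolerability questionnaire follows completion of the CLE test (6.4.4), so that secondary endpoint may miss the same people.

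**Working it through.** **Which cases are at issue.** Serious device-related events end the study (9.4, 15), so replacement does not arise for them. Section 6.3.3 excludes participants when "Head circumference is less than 50cm or greater than 63cm", so some misfit is ineligibility; misfit within 50 to 63 cm is not. A stopped test that had already given a diagnostic image is a success under 6.2.1 and is not at issue. What remains is misfit in eligible participants and non-serious device effects that stop the test before a diagnostic image.

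**Inputs.** The analysed number is 30 (9.2, set on practical grounds, so there is no sample-size calculation to reproduce). The reference proportion is 49/50 = 0.98 (9.1) and the significance level is 0.01 (9.3); the direction of the test is not stated. The number of cases, k, is not in the documents and is varied here.

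**Effect on the proportion.** Suppose all 30 analysed tests are diagnostic. With the k cases left out, the report reads 30/30. With them counted as failures it reads 30/(30 + k). The lower-tail p-value is P(X ≤ 30 | n = 30 + k, 0.98), exact binomial; the intervals are Clopper-Pearson.

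| k | Proportion | Exact 95% CI | Lower-tail p |
|---|---|---|---|
| 0 | 30/30 = 100% | 88.4–100% | 1 |
| 1 | 30/31 = 96.8% | 83.3–99.9% | 0.465 |
| 2 | 30/32 = 93.8% | 79.2–99.2% | 0.134 |
| 3 | 30/33 = 90.9% | 75.7–98.1% | 0.028 |
| 4 | 30/34 = 88.2% | 72.5–96.7% | 0.0046 |

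The p-values apply directly when all k cases are device-effect stops. The 49-in-50 reference is defined on image quality, so with misfits included they are only an illustration.

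**Effect on the planned test.**

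- Lower-tail direction (evidence of being worse than 0.98): four failures in total are needed. Three failures in 30 give p = 0.022 and four give 0.0029; four in 34 give 0.0046. These probabilities rise with n, so the threshold stays at four from n = 30 to 34. If there are no image failures, all four must be omitted cases; any image failures reduce that number.
- Superiority direction: 30/30 already gives p = 0.98^30 = 0.545, and 30/31 gives 0.873. Neither approaches 0.01, so no k changes the conclusion.

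**How readily cases could arise.** With an assumed rate r of such cases per participant, P(k ≥ 1) before 30 are analysed is 1 − (1 − r)^30, and P(k ≥ 4) comes from the negative binomial.

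| Assumed r | P(k ≥ 1) | P(k ≥ 4) |
|---|---|---|
| 1% | 0.26 | 0.0003 |
| 2% | 0.45 | 0.004 |
| 5% | 0.79 | 0.08 |
| 10% | 0.96 | 0.42 |

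**Whether 9.5 settles it.** One case is 1/31 = 3.2%, inside the 5% limit; two are 2/32 = 6.3%, outside it. But a loss caused by the headgear is not missing completely at random, and 9.5 names no outcome for it.

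**The case against.** The strongest reply concerns the stopped tests. The clinician answers the image question after the appointment, so a stopped test can still be scored. If the image was inadequate, the answer is no, which is a failure under 6.2.1. The 6.4.4 note removes only tests that failed for unrelated reasons, 9.7 keeps all eligible participants, and withdrawal under 6.5 is discretionary. This stands as far as it goes. A reader might infer that the plan has no scoring for device-stopped tests at all; the documents do not support that. The fault is a conflict: 6.5 also allows the same participant to be removed from the study and replaced.

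Second, a misfit produces no test and no image, so its absence does not distort 6.2.1 as written. That is right, and the point about misfits is the distance between endpoint and objective.

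Third, 49 in 50 is a threshold for images that are not clear and stable enough. A reader might infer that one misfit puts the device below the protocol's acceptable level. It does not, because the documents state no acceptable level for misfit or for a composite that includes it.

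Fourth, no rate of such cases is given. Head size is screened and measured again before fitting, and limited human testing without the endoscope was done (9.2). That makes cases less likely but does not say how to count one that occurs.

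**Conclusion.** The point holds. Section 6.5 allows device-caused losses to be replaced. For device-effect stops this contradicts 6.2.1, the 6.4.4 note and 9.7; for misfits it leaves the objective only partly measured. The effect is mainly on the reported proportion: one case separates 100% from 96.8%, given 30 analysed successes.

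A reader might infer that the primary test is compromised. The figures do not support that: in the lower-tail direction it takes four failures in total, and in the superiority direction nothing changes. Bias is possible and not certain, because withdrawal is discretionary and k is unknown. This should be fixed before analysis. Confidence is high that 6.5 needs reconciling with the other sections; the size of the effect depends on assumed case numbers.

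**What to change.** Change analysis wording only, leaving untouched when a test is stopped or a participant is withdrawn:

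1. In 6.5 and 9.7, state that a participant whose test was stopped for a device effect or other headgear reason stays in the primary analysis and is scored on the image: a failure if EILO could be neither confirmed nor ruled out. A replacement adds to that case and does not displace it.
2. Beside the image-based proportion, report a suitability proportion. Its denominator is all consented, eligible participants in whom fitting was attempted, with inability to wear the headgear counted as a failure. Keep the 49-in-50 test for the image-based proportion unless 9.1 is amended to say that the reference also applies to the composite.
3. Exclude withdrawals unrelated to the headgear from both proportions. List withdrawals with no stated reason separately, since 6.4.1 lets participants give none, and show the result with these counted as failures.
4. Report all withdrawals by reason, and state in 9.5 that headgear-related cases are not handled as missing data.

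The cost is small. The withdrawal reason is already recorded, but whether it is attributed to the headgear must be recorded with it. The reported proportion may be lower, and the analysed number may exceed 30.
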